#### **Protocol Specifications**

For purposes of this protocol:

All non-serious adverse reactions will be elicited and recorded at the study visit and telephone followup.

Any serious adverse events will be recorded from the day of consent and will end after the four day follow-up telephone call.

- For each SAE the following information will be collected:
  - o Full details in medical terms and case description
  - Event duration (start and end dates, if applicable)
  - Action taken
  - Outcome
  - o Seriousness criteria
  - Causality in the opinion of the investigator
  - Whether the event is considered expected or unexpected.

Initial SAE reports and any change of condition or other follow-up information should be sent via confidential email to the NCTU as soon as it is available or at least within 24 hours of the information becoming available. Events will be followed up until the event has resolved or a final outcome has been reached.

## 10.3 Recording and Reporting Unexpected Related Serious Events (URSEs)

As Leukapheresis is a routine clinical procedure to collect leukocyte samples it is not anticipated that there will URSE's. Any URSEs occurring from the intervention until 4 days post termination of the leukapheresis will be reported to the NHS REC. The NCTU, on behalf of the Sponsor, will perform this reporting.

The assessment of expectedness will be performed by the CI against the known information for the leukapheresis procedure. The reference safety information (RSI) for this study is section 9.1 - the known risks of leukapheresis. This should be used when judging expectedness.

URSEs must be reported no later than 15 calendar days after the NCTU has first knowledge of the event. Any relevant follow-up information should be sought and reported as soon as possible after the initial report.

As soon as a site suspects that a SAR may be a USRE they must contact the CI, sponsor representative and the trial manager immediately. The reporting timeframe starts at day 0 when the NCTU and/or Sponsor are in receipt of a minimum set of information:

- Sponsor study reference and study name (sponsor reference)
- Patient study number
- Date of notification of the event
- Medical description of the event
- Date and time of the onset of the event (including event end date if applicable)
- Causality assessment
- Seriousness of the event, particularly if life threatening or fatal
- An identifiable reporter (e.g., Principal Investigator)

This information must be provided by email. The site is expected to fully cooperate with the Sponsor and NCTU in order that a full and detailed report can be submitted to the NHS REC within the required timelines.

## 10.4 Responsibilities

#### **Principal Investigator**

- Recording any AEs and ARs which occur during Leukapheresis or during the 4 day follow-up period in line with the requirements of the protocol.
- Using medical judgement in assigning seriousness and causality and providing an opinion on expectedness of events.
- Ensuring that all SAEs and SARs, including URSEs, are recorded and reported to the Sponsor within 24 hours of becoming aware of the event and provide further follow-up information as soon as available.

#### **Chief Investigator**

- Clinical oversight of the safety of study participants, including an ongoing review of the risk.
- Using medical judgement in assigning expectedness to SARs on behalf of sponsor.
- Immediate review of all URSEs.

#### Sponsor

 Expedited reporting of URSEs to the REC within required timelines (may be delegated).

#### 10.5 Notification of Deaths

Only deaths that are assessed to have a causal relationship to the intervention will be reported to the sponsor. This report will be immediate.

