## **10 SAFETY REPORTING**

## 10.1 Definitions

Term	Definition				
Adverse Event (AE)	Any untoward medical occurrence in a participant, including occurrences which are not necessarily caused by or related to the intervention under study.				
Adverse Reaction (AR)	An untoward or unintended response in a participant to which is related to the intervention under study i.e. that a causal relationship between the study intervention and an AE is at least a reasonable possibility and the relationship cannot be ruled out.				
	All cases judged by either the reporting medically qualified professional or the Sponsor as having a reasonable suspected causal relationship to the study intervention qualify as adverse reactions.				
Serious Adverse Event (SAE)	
 
Results in death
 
Is life-threatening*
 
Requires inpatient hospitalisation or prolongation of existing hospitalisation
 
Results in persistent or significant disability/incapacity
 
Consists of a congenital anomaly or birth defect
 
Other important medical events that jeopardise the participant or require intervention to prevent one of the above consequences
 
				
	* - life-threatening refers to an event in which the participant was at immediate risk of death at the time of the event; it does not refer to an event which hypothetically might have caused death if it were more severe.				
Serious Adverse Reaction (SAR)	An adverse event that is both serious and, in the opinion of the reporting Investigator, believed with reasonable probability to be due to the study intervention, based upon the information provided.				
Unexpected Related Serious Event (URSE)	A serious related event, the nature and severity of which is not consistent with the known information about the intervention under study.				

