## 10.2 Recording and Reporting AEs and SAEs

All AEs and SAEs occurring from the day of consent until the four day follow up telephone call is completed must be reported. Depending on the nature of the event, the reporting procedures below

will be followed. Any questions concerning adverse event reporting will be directed to the Chief Investigator or Principal Investigator in the first instance.

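### Section 10.5 limits death reports to the sponsor to deaths judged causally related, which contradicts the rule in 10.1, 10.2 and 10.4 that every SAE is reported whatever its cause

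*Protocol*

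**What the plan says.** Section 10.5 of the protocol, on notification of deaths, consists of two sentences. The first is "Only deaths that are assessed to have a causal relationship to the intervention will be reported to the sponsor". The second sets the timing: "This report will be immediate".

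The rest of section 10 treats serious events differently:

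- **10.1 Definitions.** The first criterion for a serious adverse event is "Results in death". The adverse event definition is explicit that causality is not needed, "including occurrences which are not necessarily caused by or related to the intervention under study". For adverse reactions, either the medically qualified reporter or the Sponsor may decide that a causal link is reasonably suspected.
- **10.2, opening paragraph.** "All AEs and SAEs occurring from the day of consent until the four day follow up telephone call is completed must be reported".
- **10.2, Adverse Event.** The investigator at site assesses causality.
- **10.2, Protocol Specifications.** "Initial SAE reports and any change of condition or other follow-up information should be sent via confidential email to the NCTU", with 24 hours as the outer limit. The investigator's view of causality is one of the items collected for each SAE.
- **10.4, Principal Investigator.** The duties include "Ensuring that all SAEs and SARs, including URSEs, are recorded and reported to the Sponsor within 24 hours of becoming aware of the event".

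**The concern.** Section 10.5 is where site staff would look after a death, and it is the most specific text on the subject. Read as written, it turns the causality assessment from an item recorded in the report into a condition for telling the Sponsor at all. That assessment belongs to the site. Section 10.1 gives the Sponsor its own say on whether an event is related, but the Sponsor cannot use it for a death that it has not been told about. What is at stake is the Sponsor's oversight of the most serious kind of event, together with a protocol that gives a site two incompatible instructions for the same case.

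**Working it through.** No arithmetic applies. The check sets the reporting rules side by side for a death between consent and completion of the follow-up call.

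1. **Is the death an SAE?** Yes. Section 10.1 makes death a seriousness criterion and attaches no causality condition to it.
2. **Is it inside the general reporting rule?** Yes. Section 10.2 covers all SAEs in this window.
3. **What does each section then require?**

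| Site's causality assessment | 10.4: report to the Sponsor | 10.2: report to the NCTU | 10.5: report to the sponsor | Can 10.4 and 10.5 both be followed? |
|---|---|---|---|---|
| Related | Within 24 hours | Within 24 hours | Immediately | Yes. An immediate report also meets the 24-hour limit |
| Unrelated | Within 24 hours | Within 24 hours | Excluded | No |

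4. **Is the recipient the same?** Yes. Both 10.4 and 10.5 name the Sponsor, so the conflict is not an effect of two separate reporting lines.
5. **Is there a rule of precedence?** None was found. No section says that 10.5 adds to the SAE rule, overrides it, or applies only after the reporting window. The safety reporting diagram listed as Appendix 1 was not in the text available for review, so its routing could not be checked.

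The contradiction is therefore confined to one row: a death within the window that is judged unrelated. Related deaths are handled consistently. Deaths after the follow-up call fall outside 10.2 and are not part of the conflict.

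**The case against.** The strongest reply is that such a death would still be reported. Sections 10.2 and 10.4 require every SAE to be reported, so a site that withheld an unrelated death would breach both. Section 10.5 restricts reports to the sponsor only and leaves the NCTU route in 10.2 untouched. The NCTU reports unexpected related serious events on the Sponsor's behalf (10.3). It also monitors the study for the Sponsor, with serious adverse events as one area of focus (section 13). This stands as mitigation. A reader might infer from 10.5 that an unrelated death would vanish from the safety record, and the documents do not support that. The conflict remains, because 10.4 and 10.5 give opposite instructions about the same recipient.

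A second reply is that 10.5 was meant only as a faster, additional notice for related deaths, which its second sentence suggests. That is plausible as an intention. The opening word of 10.5 nevertheless excludes other deaths, and nothing in the section describes the notice as additional.

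Two further inferences are tempting and should not be drawn:

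- **That the Chief Investigator loses a causality review.** Section 10.4 gives the Chief Investigator expectedness for serious adverse reactions on the Sponsor's behalf, not a separate causality review. A death judged unrelated would not reach that step unless it were reclassified. What 10.5 exposes is the Sponsor's own judgement under 10.1.
- **That adverse events between screening and leukapheresis, an interval of up to 30 days, go unrecorded.** The first Principal Investigator duty in 10.4 reads "Recording any AEs and ARs which occur during Leukapheresis or during the 4 day follow-up period", which taken alone starts later than 10.2. The sentence goes on to tie that duty to what the protocol requires, 10.2 starts at consent, and the schedule in 8.7 marks adverse events at screening. The bullet is loosely worded, and no loss of recording follows. The SAE duty in 10.4, which governs deaths, has no such start point.

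**Conclusion.** Section 10.5 is wrong as written and should be corrected. For a death in the reporting window judged unrelated, it cannot be followed together with 10.4, and it undercuts the Sponsor's independent causality judgement in 10.1.

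The practical size is small. At most nine participants undergo a single leukapheresis, which the protocol describes as routine, with a follow-up call 3-4 days later. No formal statistical analysis is planned, and the primary outcome is successful leukapheresis, so no study conclusion turns on this text. The case for correction rests on what the rule says about the most serious event, not on how likely that event is.

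The conclusion assumes that the site makes the causality assessment to which 10.5 refers. Section 10.5 does not name the assessor, but 10.2 gives the task to the investigator at site. It also assumes that the Appendix 1 diagram does not settle precedence. If it does, the text of 10.5 would still need to be brought into line with it.

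**What to change.** Reconcile 10.5 with 10.2 and 10.4. Section 10.5 could state that all deaths from the day of consent to completion of the follow-up call are SAEs and are reported to the NCTU/Sponsor under the existing 24-hour rule, whatever the causality assessment. The immediate notice for deaths assessed as related can stay, worded as an addition to that rule. Check that the Appendix 1 diagram shows the same routing.

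As an optional tidy-up, start the first Principal Investigator bullet in 10.4 at consent, so that it matches the window in 10.2.

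The cost is a sentence or two in 10.5 and, if wanted, a few words in 10.4, processed through the protocol's amendment procedure. No new study procedures or data items are needed, since the SAE report already collects causality.

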## 10.6 Reporting Urgent Safety Measures

An Urgent Safety Measure (USM) is an action that the Sponsor or an Investigator may take in order to protect the subjects of a study against any immediate hazard to their health or safety. Upon implementation of an USM by an Investigator, the NCTU must be notified immediately and details of the USM given. The NCTU must inform the NHS REC within 3 days of the USM taking place in accordance with the Sponsor's/NCTU's standard operating procedures.

## 11 GMP VALIDATION PROCESS

## 11.1 Population

Data from the GMP validation of the samples from up to nine participants recruited to the study will be presented in an IMPD.

#### 11.2 Validation Process

The study is designed to validate the manufacturing process and no formal statistical analysis is planned. Qualitative data only will be presented. Quality, manufacturing and control data will be analysed in the Newcastle Cellular Therapies GMP facility and will be documented in an Investigational Medicinal Product Dossier.

Primary objective (GM Process engineering): The ToIDC product will be made at a new GMP manufacturing site and demonstrate that it is possible to produce cit-ToIDC cells of sufficient yield for clinical use. The cells collected and processed at this stage will be used to refine and assess the analytical methods used in the validation phase.

Secondary Objective (GMP Validation): The data from validation process will be used to set acceptance criteria for essential safety properties of the ToIDC cells and enable future batches to be assessed prior to use in a clinical trial. Data from this and the process-engineering phase will be presented in an IMPD for regulatory assessment.

The main points in the ToIDC product life-cycle where data will be collected and used to set expected acceptance limits are:

• Starting material (the donated sample): cell number, viability (live cells versus dead cells), purity (percentage of different populations of cells).

• Final ToIDC product: Cell number, viability, yield (number compared to cells at the start of the process), purity (number of ToIDC cells compared to non-ToIDC cells) potency (ability of cells to function as intended)

The properties of the cells in the final product specification will also be measured at additional time points during the manufacture of the ToIDC product for example before and after adding a label to trace the cells and before and after cryopreserving (freezing) the cells.

The analysis at each point may also be performed in duplicate or triplicate as and when required for validation of the analytical method according to current GMP regulatory expectations.

## 11.3 Sample Size Calculations

No formal sample size calculation has been carried out for this study. Up to nine participants will undergo leukapheresis to obtain up to 6 adequate samples to complete the GMP validation work. The reason for this is the GMP validation master plan dictates that 3 process engineering runs and then 3 full validation runs are performed to qualify a manufacturing process before clinical use. It may be possible to perform the process engineering runs using blood products from the blood bank, if this is the case then participants would not be recruited to provide leukapheresis samples to these runs. However, if the use of blood products for the process engineering runs is unsuccessful then leukapheresis samples will be obtained from participants. Leukapheresis samples from participants will be used to perform the 3 full validation runs. This number is taken from EU guidance on advanced therapy medicinal product manufacture (EudraLex Vol. 4 GMP Guidelines on GMP specific to ATMPs) which states: 'It is generally accepted that, as a minimum, three consecutive batches manufactured under routine conditions constitute a validation of the process'. As the toIDCs have not previously been manufactured using the same method (i.e. including peptides, F labelling and cryopreservation) an additional 3 process engineering runs will be performed to provide material to validate the safety testing prior to use and ensure that any refinements to the manufacturing process or QC testing are incorporated before the final validation runs.

## 12 DATA HANDLING

## 12.1 Data Collection Tools and Source Document Identification

Data collected on screening, recruitment and follow-up will be entered by the site staff onto study specific worksheets which will then be securely sent to NCTU. Data from the worksheets will be entered by NCTU staff into a password protected data repository. Participants will be identified on study documentation and the data repository by a unique study identifier. Data management will be the responsibility of the Newcastle Clinical Trials Unit who will run validation and consistency checks on the data and will perform Quality Control (QC) checks on the transfer of data from worksheets to the data repository. Any data queries will be communicated to site and resolved as appropriate. The product validation data will be the responsibility of the Newcastle Cellular Therapies Facility and will not be held in the study data repository.

## 12.2 Data Handling and Record Keeping

Overall responsibility for data collection lies with the Chief Investigator. Data will be handled, computerised and stored in accordance with The Data Protection Act 2018 and General Data Protection Regulations (GDPR) 2018. The overall quality and retention of study data is the responsibility of the Chief Investigator. All study data will be retained in accordance with the applicable regulations and local policies.

#### 12.3 Access to Data

The study data and patient medical records may be reviewed for monitoring by NCTU, or for audit purposes by the Newcastle upon Tyne Hospitals NHS Foundation Trust or NCTU.

Clinical information will not be released without the written permission of the participant, except as necessary for monitoring and auditing by the Sponsor, its designee or the REC. The PI and research site staff involved with this study may not disclose or use for any purpose other than performance of the study, any data, record, or other unpublished, confidential information disclosed to those individuals for the purpose of the study. Data will be accessed only by the study team involved with the validation, there will be no research findings for wider dissemination.

## 12.4 Archiving

In accordance with the UK Policy Framework for Health and Social Care Research, Sponsor and NCTU SOPs and other applicable regulatory requirements all study data will be retained for 30 years. Authorisation will be obtained from the Sponsor at the end of the archiving period to destroy the study documentation.

## 13 MONITORING, AUDIT & INSPECTION

Study monitoring will be undertaken by Newcastle Clinical Trials Unit, on behalf of the Sponsor, to ensure the study is conducted in accordance with the Research Governance Framework. The main areas of focus will include consent, serious adverse events, and essential documents in study files. A risk assessment of the study will be carried out at the outset and the level of monitoring will be commensurate with the perceived risk. A study monitoring plan will be developed based upon the risk assessment and will be agreed by the Trial Management Group and the Sponsor. Monitoring will consist of a combination of site self-monitoring and off-site monitoring:

- Completion by site staff of a self-monitoring form, provided by the NCTU, covering recruitment status, study participant documentation, the content of the study file and a review of any SAE forms.
- A consent proforma returned to the NCTU by the site will be used to verify that the appropriate
  version of the consent form has been used and all relevant sections have been completed
  correctly.

- An eligibility checklist for all participants entered in the study will be completed which will include a signed statement of eligibility by the PI and filed in the medical notes.
- Study sample logs will be reviewed centrally.

Study oversight will be provided by the Trial Management Group.

The study may be subject to audit by representatives of the Sponsor or inspection by other regulatory bodies. The investigator site will permit study-related monitoring, audits and regulatory inspection including access to all essential and source data relating to the study if required.

## 14 ETHICAL AND REGULATORY CONSIDERATIONS

## 14.1 Research Ethics Committee Review and Reports

The NCTU will obtain a favourable ethical opinion from an NHS Research Ethics Committee (REC) prior to the start of the study. All parties will conduct the study in accordance with this ethical opinion.

The NCTU will notify the REC of all required substantial amendments to the study and those non-substantial amendments that result in a change to study documentation (e.g. protocol or patient information sheet). Substantial amendments that require a REC favourable opinion will not be implemented until this REC favourable opinion is obtained. The NCTU will notify the REC and Sponsor of any serious breaches of GCP or the protocol, urgent safety measures or USREs that occur during the study.

An annual progress report will be submitted each year to the REC by NCTU until the end of the study. This report will be submitted within 30 days of the anniversary date on which the original favourable ethical opinion was granted.

The Sponsor will notify the REC of the early termination or end of study in accordance with the required timelines.

#### 14.2 Peer Review

This study is funded by a grant from Arthritis Research UK and was subject to peer review of the research proposal before funding was awarded.

This protocol has been reviewed and authorised by the Sponsor, Chief Investigator and Newcastle Clinical Trials Unit.

#### 14.3 Public and Patient Involvement

The study participant information will be reviewed by rheumatoid arthritis patient groups.

## 14.4 Regulatory Compliance

The study will be conducted in accordance with the UK Policy Framework for Health and Social Care Research. Before any site can enrol patients into the study, that site must have received NHS permission from the NHS Research & Development department.

## 14.5 Protocol Compliance

Prospective, planned deviations or waivers to the protocol are not allowed in this study and must not be used. Protocol deviations, non-compliances and breaches are departures from the approved protocol. These events should be documented on the deviation tracking log (this will be provided as part of the ISF). NCTU will ask the site to provide copies of their deviation tracking log periodically and before any monitoring visits

If the deviation constitutes a violation, the site must complete a protocol violation form (a blank template will be provided to the site as part of the ISF) and send a copy of this completed form to the Trial Manager in NCTU within 3 working days. The violation must also be entered on to the deviation tracking log.

Unintentional protocol deviations will be documented and reported to the CI and sponsor. Where necessary, Corrective and Preventative Actions (CAPA) will be implemented. Deviations that are found to frequently recur at a site are not acceptable and could be classified as a serious breach

